# 9 STATISTICS

### 9.1 Estimation of sample size

In previous studies using the same techniques (i.e. C-acetate PET scan and echocardiography), beta-blockers in drug-naïve patients increased cardiac efficiency by 45% (Beanlands 2000). In later studies using e.g. new biventricular pacing techniques in previously medicated patients, the cardiac efficiency was improved by 20% (Sundell 2004). Therefore, we assume that the clinically significant change in cardiac efficiency in medicated patients would be about 20%. In our previous studies in patients with heart failure (Nesterov 2015, Tuunanen 2008), the same patients were studied twice in the interval of 3 months, the coefficient of variation (CV%) of Kmono in placebo group was 18.4% and in efficiency 19.7%. Based on sample size calculations, in order to detect a 15% change in cardiac efficiency, 27 subjects would need to be included in each treatment arm (assuming  $\alpha = 0.05$  and  $\beta = 0.2$ ). Due to potential drop outs during the study, the target is to enroll 30 + 30 subjects in the treatment arms.

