
### 4.2 Randomization and blinding

The subjects will be randomized in a 1:1 ratio to one of the two treatment arms, either the sacubitril/valsartan treatment arm or the valsartan treatment arm. Stratified randomization will be used to achieve similar groups in terms of patients with renal insufficiency (GFR 45-60 or >60 mL/min/1.73m^2) and/or diabetes mellitus (on insulin or oral glucose-lowering therapy, no more than 50 % of patients in the study are allowed to be diabetic). The baseline HF therapy (the number of subjects that are on valsartan 160 mg BID at the time of randomization) will also be taken into account during randomization.

Study drug packages will be provided from Novartis with removable labels stating the treatment. Treatment allocation will be done by an un-blinded member of the study team who will remove the labels stating the treatment before distributing the study drug packages to the subjects.

The randomization will be generated by an independent statistician at using SAS®.

Sealed envelopes containing the individual treatment codes (randomization number and the corresponding treatment) will be stored adjacent to the investigational medicinal products (IMPs) until the end of the trial. In case of an emergency requiring immediate knowledge of the treatment administered, the code of an individual subject may be opened. The reasons for opening the code have to be documented and the subject has to be discontinued from the study. The study monitor and the sponsor should be immediately informed about breaking of the treatment code.

This study will be conducted in a double-blinded fashion regarding the treatment (i.e. sacubitril/valsartan or valsartan). As the sacubitril/valsartan and valsartan tablets differ in appearance, the study has to be performed in a double-dummy manner with the subjects taking one active tablet and one placebo tablet BID. The different

strengths of the two study drugs are not identical in appearance so the possible dose modification(s) during the treatment period cannot be performed in a blinded manner. However, the up-titration step will be aligned in both treatment arms – the subjects will start on valsartan (80 mg BID or 160 mg BID) or sacubitril/valsartan (100 mg BID) and there will be only one scheduled up-titration visit after the randomization. The subjects that start from valsartan 160 mg BID will have similar scheduled visit but will stay on the same dose.

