# 9.2.2 Statistical hypotheses

The study hypothesis is that short-term therapy with sacubitril/valsartan added on standard HF therapy improves cardiac efficiency in patients with systolic HF. In order to test this, the null hypothesis is formulated as follows:

 $H_0: \mu_1 = \mu_2$ 

which will be tested against the alternative hypothesis:

 $H_A$  :  $\mu_1 \neq \mu_2$ 

where  $\mu_1$  and  $\mu_2$  are the mean values of change in cardiac efficiency in the two treatment arms, as measured by PET and echocardiography at visit 3. The null hypothesis will be tested based on a two-sided test and a significance level of 0.05.

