# 2.4 Analysis supporting primary objective(s)

# 2.4.1 **Primary endpoint(s)**

The primary endpoint is this study is change from baseline in cardiac efficiency at visit 3, after 6 weeks of stable sacubitril/valsartan or valsartan treatment.

The definition of cardiac efficiency is (LV work/gram of tissue) / Oxygen consumption. Where LV work/gram of tissue is obtained by Echocardiography as (SBP x SV x HR) / LV mass, and Oxygen consumption is obtained by Cacetate PET as tracer as a mono exponential clearance rate of Cacetate (kmono)

So, cardiac efficiency is calculated based on the following formula:

Myocardial efficiency = ((SBP x SV x HR)/LV mass)/Kmono

Where

- SBP : Systolic blood pressure during PET
- SV : Stroke volume (Echocardiography)
- HR : Heart rate
- Kmono: Mono-exponential clearance rate (11C-acetate PET- scan)
- LV mass: Left ventricular mass

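### Is the design underpowered because 27 per arm was derived from an undefined 19.7% coefficient of variation?

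*Protocol*

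**What the plan says.** Protocol 9.1 and SAP section 3 carry the same paragraph. It calls on two earlier effects, 45% with beta-blockers in untreated patients and 20% with biventricular pacing in treated patients, and concludes that "we assume that the clinically significant change in cardiac efficiency in medicated patients would be about 20" per cent. For variability it cites the team's own earlier heart failure studies, in which "the same patients were studied twice in the interval of 3 months", and reports that the CV of Kmono "in placebo group was 18.4% and in efficiency 19.7" per cent. It then states that "in order to detect a 15% change in cardiac efficiency, 27 subjects would need to be included in each treatment arm", with alpha 0.05 and beta 0.2, and raises the target to 30 per arm to allow for dropout.

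The comparison being sized is given elsewhere. The endpoint is "change from baseline in cardiac efficiency at visit 3" (SAP 2.4.1). Protocol 9.2.2 sets equality of mean change in the two arms as the null hypothesis and adds that "The null hypothesis will be tested based on a two-sided test and a significance level of 0.05". Allocation is 1:1 (Protocol 4.2). The primary analysis is an ANCOVA of change from baseline with treatment, strata and baseline efficiency, reported as a treatment difference with a 95% confidence interval (Protocol 9.2.6, SAP 2.4.2).

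The paragraph leaves out the type of CV, the formula, any baseline to follow-up correlation, and an explicit statement that 15% is a difference between arms.

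**The concern.** A CV quoted right after a statement that the same patients were scanned twice can be read as test-retest variability of one measurement. The endpoint is a difference of two measurements, so its SD would then be larger by a factor of sqrt(2), and 27 per arm would fall well short of 80% power for 15%.

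There is also a coincidence in the arithmetic. A one-sample paired calculation with that larger SD returns the same 27.08 as the two-sample calculation with 19.7. Reproducing 27 therefore does not prove that the between-arm comparison was the one sized. Finally, an exact t calculation with SD 19.7 gives slightly less than 80% at 27 per arm.

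At stake is how a null result is read. A reader who relies on 80% power for 15% would take the trial as fairly strong evidence against an effect of that size.

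**Working it through.** **Inputs.** Difference 15%, CV 19.7%, alpha 0.05, beta 0.2, 27 completers per arm (Protocol 9.1); two-sided test (Protocol 9.2.2); 1:1 allocation (Protocol 4.2); baseline-adjusted ANCOVA (Protocol 9.2.6). The correlation rho between baseline and visit 3 is not in the documents, so 0.5, 0.7 and 0.9 are assumed as a range, with equal variances at the two visits.

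**The plan's own figure.** n per arm = 2 x (1.960 + 0.8416)^2 x (19.7/15)^2 = 27.08. Power at 27 by the normal approximation: 15 / (19.7 x sqrt(2/27)) = 2.798, and Phi(2.798 - 1.960) = 79.9%. Dropout: 27 / 0.9 = 30. All three agree with the plan.

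**The small shortfall.** The noncentral t version of the same unadjusted comparison gives 78.4% at 27 and 82.6% at 30 per arm, and needs 29 per arm for 80%. The 1.5-point gap at 27 comes from the choice of formula. It also describes an unadjusted comparison, whereas the trial will adjust for baseline.

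**What ANCOVA does under each reading.** Let S be the SD at a single visit. The SD of change is S x sqrt(2(1 - rho)), and the ANCOVA residual SD is S x sqrt(1 - rho^2).

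- A: 19.7 is the SD of change. Residual SD = 19.7 x sqrt((1 + rho)/2).
- B: 19.7 is the within-subject SD of one measurement. SD of change = 19.7 x sqrt(2) = 27.9; residual SD = 19.7 x sqrt(1 + rho).
- C: 19.7 is the between-subject SD at one visit. Residual SD = 19.7 x sqrt(1 - rho^2).

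Noncentral t power for a 15% difference, 27 per arm, 52 degrees of freedom:

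| Reading | rho 0.5 | rho 0.7 | rho 0.9 |
|---|---|---|---|
| A: residual SD | 17.1 | 18.2 | 19.2 |
| A: power | 88.7% | 84.6% | 80.4% |
| B: residual SD | 24.1 | 25.7 | 27.2 |
| B: power | 61% | 56% | 51% |
| C: residual SD | 17.1 | 14.1 | 8.6 |
| C: power | 89% | 97% | above 99% |

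Under B without baseline adjustment, power is 49%. Spending a few degrees of freedom on covariates hardly matters: with SD 19.7, 49 instead of 52 degrees of freedom moves power from 78.4% to 78.3%.

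**Detectable difference under B.** With 80% power at 27 per arm, ANCOVA detects 18.7%, 20.0% and 21.1% for rho 0.5, 0.7 and 0.9 (21.6% unadjusted). Power for a 20% difference is 85%, 80% and 76%.

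**The paired coincidence.** One-sample n with SD 27.9 = (1.960 + 0.8416)^2 x (27.86/15)^2 = 27.08. It must equal the two-sample result, because the factor 2 moves from the number of arms into the variance. It therefore cannot tell the two routes apart.

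**The case for a change.** The strongest case for acting is that one undefined term moves power for 15% from about 50% to well above 80%. A CV reported next to repeat scans invites the test-retest reading. On that reading the stated power is wrong, 42 to 53 per arm would be needed under ANCOVA (rho 0.5 to 0.9), and enrolling 30 would not rescue it: even with all 30 completing, power is 66%, 60% and 56%. The sponsor calls the sources its own earlier studies, so it should be able to say which CV was used, and a clarifying sentence costs little.

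The arithmetic stands, and so does the remark that the paragraph is underspecified. What does not stand is the step from one possible reading to a failed design. An SD of paired change also comes from measuring the same patients twice, and it is the reading under which 27 follows directly for the two-arm comparison the plan describes. Only the cited studies could decide between the readings, and they are outside the documents. Nor is 78% an upper limit on the favourable side: readings A and C both reach 80% or more over the assumed range once the planned adjustment is applied. Replacing the stated 80% with 78% would swap a supportable figure for one that belongs to an analysis the trial will not run.

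**Conclusion.** No change follows. The stated size reproduces from the plan's own inputs (27.08 per arm, 79.9% power at 27). On the reading that leads to it directly, the planned ANCOVA gives 80% to 89%. A shortfall to 51% to 61% arises only if 19.7% is a single-measurement within-subject CV, which the text permits but does not establish. Both ranges rest on an assumed rho of 0.9 to 0.5 and equal variances at the two visits.

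Even on the unfavourable reading the trial keeps its purpose. It would have 80% power for about 19% to 21%, around the 20% the plan treats as clinically significant; the 15% used for sizing is the more demanding target. A null result will be judged from the 95% confidence interval for the treatment difference, which reflects the variability actually observed and makes the planning CV irrelevant to interpretation. That 15% is a between-arm difference can be inferred from the hypothesis in Protocol 9.2.2.

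What remains is missing detail in the sample size paragraph. Filling it in would alter no analysis, patient number or decision rule.

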### 9.2 Statistical methods

A summary of the statistical methods is described below.

9.2.1 Statistical Analysis Plan

Before unblinding the study data a separate statistical analysis plan (SAP), which will provide the technical details of the statistical analysis outlined below, will be prepared by the biostatistics service provider, and approved.

# 9.2.2 Statistical hypotheses

The study hypothesis is that short-term therapy with sacubitril/valsartan added on standard HF therapy improves cardiac efficiency in patients with systolic HF. In order to test this, the null hypothesis is formulated as follows:

 $H_0: \mu_1 = \mu_2$ 

which will be tested against the alternative hypothesis:

 $H_A$  :  $\mu_1 \neq \mu_2$ 

where  $\mu_1$  and  $\mu_2$  are the mean values of change in cardiac efficiency in the two treatment arms, as measured by PET and echocardiography at visit 3. The null hypothesis will be tested based on a two-sided test and a significance level of 0.05.

# 9.2.3 Data sets to be analyzed

The following analysis sets will be used for the statistical analysis and presentation of data:

- **The safety set** will consist of all randomised subjects who received at least one dose of the study medication in the treatment period, provided that there was at least one safety follow-up performed for the subject.
- The full analysis set (FAS) will consist of all randomised subjects who have received at least one dose of study medication in the treatment period and have at least one post-baseline assessment of any efficacy endpoints.
- **The per protocol set (PPS)** will consist of all subjects in the FAS who received at least 75% of the study drug doses, and do not have any other major protocol violations which will affect the assessment of efficacy. Major/important protocol violations may include, but are not limited to, the following:
  - Non-fulfillment of all inclusion criteria
  - o Fulfillment of at least one exclusion criteria
  - Use of certain concomitant medications (this will be judged on a case to case basis, depending on extent of treatment)

The final criteria for PPS, regarding which protocol deviations that warrant exclusions, will be determined when all data on protocol violations/deviations are available and before breaking the blind. The FAS is considered as the primary analysis dataset, and will be used for all primary and secondary efficacy analyses. The primary efficacy analysis will be repeated using the PPS. Any significant discrepancy between the results from the FAS and the PPS will be analysed and discussed.

Baseline presentations will be based on the safety set.

Safety presentations will be based on the safety set

9.2.4 General statistical considerations

All data will be analyzed using summary statistics and listed. Summary statistics will include at least the number of subjects, mean, standard deviation, median, minimum and maximum for continuous variables, and frequencies and percentages for categorical variables. Geometric mean, standard deviation and coefficient of variation will also be presented, when appropriate. All summary statistics will be presented by treatment and dose level. All data collected will be listed by subject and dose level. In addition, analysis of covariance (ANCOVA) will be used for statistical analysis, when appropriate. Other statistical analyses may also be implemented, as described in the SAP.

9.2.5 Demographic and baseline characteristics

All relevant demographic and baseline characteristics will be summarized using descriptive statistics. The number and reasons for withdrawals and discontinuations

will be listed and tabulated by treatment and dose level. Separate listings will be provided for subjects screened but not included in the study (screening failures).

### 9.2.6 Analysis of efficacy variables

All efficacy variables will be tabulated using summary statistics as described in section 9.2.4, including both statistics for observed levels by visit and changes from baseline.

### **Primary Endpoint**

The primary endpoint, change from baseline in cardiac efficiency after 6 weeks on stable sacubitril/valsartan or valsartan therapy, will be analyzed by an ANCOVA including treatment and stratification as independent factors and covariate adjustment for baseline cardiac efficiency. From this model, the within treatment group (sacubitril/valsartan-valsartan) changes will be estimated by least square means and the corresponding treatment difference between treatments will be calculated with a 95% confidence interval and p-value. In addition, treatment by stratification interaction analyses will be performed for the primary efficacy parameters in order to estimate within stratification group differences. For both the baseline visit and visit 3, the results will be also summarized using descriptive statistics, with the visit 3 results to be summarized also by dose level and treatment arm.

# Exploratory Endpoints

The changes in the following cardiac and systemic hemodynamics parameters will be evaluated as exploratory efficacy endpoints: EF, NT-proBNP, systemic BP, SVR, coronary vascular resistance and cardiac oxygen consumption. The change from baseline in these parameters after 6 weeks on stable sacubitril/valsartan or valsartan therapy will be analyzed by an ANCOVA including treatment and stratification as independent factors and covariate adjustment for baseline cardiac efficiency. From this model, the within treatment group (sacubitril/valsartan-valsartan) changes will be estimated by least square means and the corresponding treatment difference between treatments will be calculated with a 95% confidence interval and p-value. For both the baseline visit and visit 3, the results will be also summarized using descriptive statistics, with the visit 3 results to be summarized also by dose level and treatment arm.

### 9.2.7 Analysis of safety variables

### 9.2.7.1 Evaluation of adverse events

AEs reported during the study will be classified by system organ class (SOC) and preferred terms (PT) using the MedDRA coding system. AEs will be displayed in a frequency table by dose level and treatment arm. The number and proportion (%) of subjects having each AE will be tabulated by SOC and PT and dose level. Severity of the AEs (mild, moderate, severe) and causality to the study treatment will be

tabulated with subject and event counts. SAEs and other significant AEs will be evaluated case by case.

AEs occurring before and after the initiation of the double-blind treatment period will be reported separately.

### 9.2.7.2 Clinical safety evaluations

The actual values of systolic and diastolic BP and HR and their changes from baseline will be evaluated with descriptive statistics by dose level and treatment arm. There will be two separate baseline values defined for the BP and HR measurements: the first BP and HR baseline value will be the one taken on the first screening visit. The subsequent BP and HR measurements during the screening/run-in period will be compared to this. The subsequent BP and HR measurements P and HR measurements during the the one taken before randomization at the baseline visit. The subsequent BP and HR measurements during the double-blind treatment period will be compared to this.

### 9.2.7.3 Clinical safety laboratory evaluations

All laboratory safety variables and their changes from baseline will be evaluated and summarized using descriptive statistics by dose level and treatment arm. There will be two separate baseline values defined for the safety laboratory assessments: the first safety laboratory baseline values will be the ones taken on screening visit 1. The subsequent laboratory results obtained during the screening/run-in period will be compared to these. The second safety laboratory baseline values will be the ones taken at the baseline visit. The subsequent laboratory results obtained during the double-blind treatment period will be compared to these. Laboratory values will also be categorized into low, normal and high according to their reference ranges. Clinically significant laboratory abnormalities and any additional laboratory tests taken for subject safety will be listed and reported in the study report.

### 9.3 Interim analyses

There will be no planned interim analyses during the study. The investigators and the sponsor will monitor subject safety and efficacy results on an ongoing basis.

# 9.4 Software

Statistical analysis will be performed and tables and subject data listings will be prepared using SAS®.

### 10 DATA MANAGEMENT

Data management and handling of data will be conducted according to the studyspecific Data Management Plan (DMP) in line with ICH guidelines standard operating procedures.

### 10.1 Database design

The trial database and data entry screen design, as well as edit checks will be defined according to the corresponding eCRFs and the study protocol.

### 10.2 Data entry

Flow of trial data and procedures regarding data handling will be described in detail in the DMP. Data will be collected on eCRFs specifically designed for this study. eCRF completion guidelines will be provided to enable accurate data entry.

The investigator or designated study center personnel will enter subject data into the eCRFs. Only persons authorized by the investigator to make original eCRF entries will be allowed to make corrections. The eCRF will have an audit trail with appropriate functionality for data capture, tracking and documentation of any queries or changes. Electronic signatures will be used to lock the data and identify the person entering or changing the data.

All eCRF entries should be verifiable from the study records. Definition of source data is agreed in a written source data agreement document before study start.

Authorized persons will code medical history and current medical conditions, AEs and concomitant treatments using standard coding dictionaries.

# 10.3 Data validation and query management

Data validation or data cleaning procedures will be designed to assure the validity and accuracy of the study data. A Data Validation Plan will specify the data checks that are performed on subject data to raise data discrepancies, and define the electronic edit checks, and data validation queries created for the trial. Validation and data queries will be handled by DM team. All trial specific and standard data validation programming will be tested in a separate testing environment prior to use on production data.

# 10.4 Medical encoding

AEs and medical history verbatim terms will be encoded using MedDRA, latest version available when approving the DMP. Concomitant Medications verbatim terms will be encoded using the World Health Organization Drug Dictionary (WHO DD), most recent version held by the DM vendor.

### 10.5 Data lock

Individual pages in the eCRFs may be locked on an ongoing basis during the study. A field may be locked after all necessary actions defined for that particular field have been completed. The fields may be unlocked if further updates are needed.

### 10.6 Database closure

All data entry, verification, medical encoding and data validation activities will be finalized before final database lock. Quality control activities will be completed to acceptable error rates. All unnecessary user privileges to the study data will be removed, except for the Data Manager who will perform the database closure. Before database closure reconciliation will be performed between the SAEs entered in the Safety database and the study database. After database closure, the database will be exported as SAS® data sets.

The locked database will be used in the final statistical analyses for study reporting. Any deviations, i.e. discrepancies and additions from the process defined in the DMP, will be described in a study specific Data Management Report.

